# Synopsis

## **Primary Objective**

Evaluate the effectiveness of an interactive online module series to train staff involved in the care of women with gestational diabetes

## **Secondary Objectives (if applicable)**

Conduct a preliminary validation of a newly developed measure to assess self-efficacy to provide diabetes education

Assess adoption of the modules and retention in the overall training

## **Study Duration**

Participants were able to complete the four modules at their leisure and given the opportunity to enter a drawing for a \$40 Visa gift card if they completed training within 3 months.

## **Study Design**

Prospective, single arm, pre/post training evaluation

## **Study Population**

### Inclusion Criteria:

Clinic staff: nurses (RN, LPN, BSN), community health workers, and others involved in maternal child health care

### Exclusion Criteria:

Clinic staff: individuals not involved in maternal child health care or who do not consent to participate in study

## **Number of Participants**

100 individuals will be recruited to complete anonymous pre and post evaluations with 4 online training modules

## **Number of Study Sites**

Washington University School of Medicine will be the primary study site. Collaborators at Affinia Healthcare are involved in the development of the modules. Individuals will complete training online from the comfort of their home or workplace

## **Primary Outcome Variables**

The primary outcome is change in score on the self-efficacy to provide diabetes education scale (newly developed) before and after completing the 4 module training.

**Secondary and Exploratory Outcome Variables (if applicable)**

- 1) Score change on Diabetes Knowledge test (overall and on subscores tied to content of each of 4 modules)
- 2) Score change on 3 subscales of the Diabetes Attitudes Scale-3  
Patient Autonomy  
Value of Tight Control  
Importance of Specialized Training
- 3) Score change on Intention to Recommend Diabetes Prevention Measures Questionnaire (Newly Developed)
- 4) Percent of individuals accessing each module and pre-and post-assessments
- 5) Validation of Self Efficacy for Providing Diabetes Education Scale  
Correlation of baseline scale scores and General Self Efficacy Scale and Physician Teaching Motivation Questionnaire
- 6) Internal reliability statistics for all scales (Cronbach's alpha)

# 1 - Introduction

## 1.1 Introductory Statement

Type 2 diabetes is a growing public health challenge and gestational diabetes predicts this preventable chronic disease at an early age. Half of all women with gestational diabetes will go on to develop type 2 diabetes without intervention. There are clear opportunities to intercede during and after pregnancy to prevent type 2 diabetes; however, it is difficult to operationalize these interventions in low resource settings and traditional healthcare models.

This study examines changes in self-efficacy, knowledge, attitudes and intentions among individuals who currently work with women who have pregnancies complicated by gestational diabetes, before and after completing online interactive education modules created by the research team.

## 2 - Background

### 2.1 Background/prevalence of research topic

GDM is an important public health problem as a diagnosis of GDM increases risks for mother and baby during pregnancy and delivery and increases the lifetime risk of maternal T2DM by 7 fold. Counseling on nutrition, physical activity, and modest weight gain to meet blood sugar targets is the cornerstone of GDM management during pregnancy. However, many Federally Qualified Health Centers, which serve as safety-net providers in under-resourced communities are not able to maintain certified diabetes educators and nutritionists on staff. Hence, many women do not receive structured diabetes self-management and nutrition education. The postpartum period is a high-risk transition of care; insurance coverage and health care providers often change, childcare responsibilities increase, and glucose abnormalities persist in a significant proportion of women with GDM after pregnancy. Despite professional guideline recommendations, there are substantial barriers to providing adequate medical nutrition therapy and diabetes self-management education to women with GDM, particularly during the pregnancy to postpartum transition. Clinic staff can be trained with modules covering the core principles of diabetes management during pregnancy and diabetes prevention for the future. As such, this study sought to evaluate such training provided in an online forum.

# 3 - Rationale/Significance

## 3.1 Problem Statement

Despite professional guideline recommendations, there are substantial barriers to providing adequate medical nutrition therapy and diabetes self-management education to women with GDM, particularly during the pregnancy to postpartum transition.

## 3.2 Purpose of Study/Potential Impact

Clinic staff can be trained with modules covering the core principles of diabetes management during pregnancy and diabetes prevention for the future. The purpose of this study was to evaluate the effectiveness of this online training.

## 3.3 Risk and Benefits

### 3.3.1 Risks

Risks of our study are minimal. Participation in the study is anonymous. Individuals who wish to be entered into the drawing for Visa gift card provide identifiers including social security number but this information is not linked to survey information.

### 3.3.2 Potential Benefits

Participants in the intervention will receive education and support which may improve their ability to take care of women with GDM and prevent future type 2 diabetes.

There are many potential benefits to the population of low-income women with GDM, healthcare providers and society in terms of knowledge to be gained. The online modules can be adapted to various education settings in the future.

# 4 - Study Objectives

## 4.1 Hypothesis

Our central hypothesis is that completing online interactive training modules on GDM will result in improved self-efficacy for providing diabetes education, improved GDM knowledge, improved attitudes toward patient autonomy, the value of tight control, and the need for specialized training, and increased intentions to recommend diabetes prevention measures.

## 4.2 Primary Objective

Evaluate the effectiveness of an interactive online module series to train staff involved in the care of women with gestational diabetes.

## 4.3 Secondary Objectives (if applicable)

Conduct a preliminary validation of a newly developed measure to assess self-efficacy to provide diabetes education

Assess adoption of the modules and retention in the overall training

# 5 - Study Design

## 5.1 General Design Description

All healthcare professionals will undergo the same procedures. After reading the instructions/what to expect page, participants will first create a personal ID code that will allow their responses to be linked, but protect their identity. Next, they will decide if they would like to participate in the research study. If they elect to participate in the research, they will complete questionnaires related to GDM knowledge, both general self-efficacy and self-efficacy to provide diabetes education, teaching motivation, intention to recommend postpartum diabetes screening, and diabetes attitudes. They will also complete a demographics questionnaire. Next, all participants will complete an approximately 4-hour online GDM training at their leisure. The online training will be composed of 4 modules covering the following topics: 1) GDM Disease and Diagnosis, 2) Practical nutrition and exercise for women with GDM, 3) Blood sugar monitoring and medication for women with GDM, 4) Future Diabetes - risk, screening, and prevention.

At the conclusion of module one, participants should be able to 1) Define gestational diabetes (GDM) & how it is diagnosed in the United States. 2) Compare changes in blood sugar control during normal pregnancy and GDM 3) Identify risk factors for GDM 4) Summarize the consequences for uncontrolled GDM for mom & baby. At the conclusion of module two, participants should be able to 1) define recommendations for weight gain during pregnancy 2) describe types of nutrients and examples of each 3) apply strategies for meal planning including cost concerns 4) design alternative plans for different dietary preferences 5) explain exercise recommendations during pregnancy 6) create a patient-centered trimester-specific physical activity plan. At the conclusion of module three, participants should be able to 1) describe blood sugar monitoring recommendations and goals in women with GDM, 2) Identify the risks and common symptoms of hypoglycemia and determine the appropriate treatment for these events, 3) Explain GDM treatment options including recommended medications. At the conclusion of module four, participants should be able to 1) Assess patients' risk of future diabetes mellitus, 2) describe current postpartum diabetes screening recommendations, 3) construct a patient-centered plan to minimize risks of future diabetes mellitus. Each module will feature questions within the module to engage with the participant and conclude with a post-test module specific knowledge assessment/review. The research team will collect all responses to these questions to assess the effectiveness of the modules. Information sources for the development of these modules include guidelines from the American Diabetes Association, Academy of Nutrition and Dietetics, American College of Obstetricians and Gynecologists, USDA Center for Nutrition Policy and Promotion, and primary literature.

After the training is complete, patients who elected to participate in the research, will repeat the GDM knowledge, self-efficacy to provide diabetes education, intention and diabetes attitudes assessments.

Items for each survey will be selected from previously validated measures and/or created by the PI. Items will be selected at the PI's discretion. All surveys and responses will be housed on Qualtrics. Participants will enter/create their unique personal ID before both survey sessions and before each education module. Participants may elect to complete the education training, but decline the option to participate in research.

If both the pre-assessment surveys and the post-assessment surveys are completed within 3 months, participants will be eligible to provide their information to be entered to win a \$40 Visa gift card. This identifiable information will only be collected to adhere to WashU institutional tax guidelines. This information will be collected using REDCap and will be stored separately from the research data.

### **5.1.1 Study Date Range and Duration**

Recruitment will start approximately June 1, 2020 and continue until 100 participants are recruited.

Primary outcome completion anticipated: August 2022

Secondary outcome completion anticipated: August 2022

### **5.1.2 Number of Study Sites**

Washington University School of Medicine will be the primary study site. Individuals will complete the modules online in the comfort of their homes/workplaces.

## **5.2 Outcome Variables**

### **5.2.1 Primary Outcome Variables**

The primary outcome is change in score on the self-efficacy to provide diabetes education questionnaire before and after completing the 4 module training. This was a newly developed measure

### **5.2.2 Secondary and Exploratory Outcome Variables (if applicable)**

- 1) Score change on Diabetes Knowledge test (overall and on subscores tied to content of each of 4 modules)
- 2) Score change on 3 subscales of the Diabetes Attitudes Scale-3
  - Patient Autonomy
  - Value of Tight Control
  - Importance of Specialized Training
- 3) Score change on Intention to Recommend Diabetes Prevention Measures Questionnaire (Newly Developed)
- 4) Percent of individuals accessing each module and pre-and post assessments
- 5) Validation of Self Efficacy for Providing Diabetes Education Scale
  - Correlation of baseline scale scores and General Self Efficacy Scale and Physician Teaching Motivation Questionnaire
- 6) Internal reliability statistics for all scales (Cronbach's alpha)

## **5.3 Study Population**

### **5.3.1 Number of Participants**

100 participants will be recruited for the study.

### **5.3.2 Eligibility Criteria/Vulnerable Populations**

Inclusion Criteria:

Clinic staff: nurses (RN, LPN, BSN), community health workers, and others involved in maternal child health care

Exclusion Criteria:

Clinic staff: individuals not involved in maternal child health care or who do not consent to participate in study

# 6 - Methods

## 6.1 Intervention

### 6.1.1 Description of Intervention

Individuals will be provided with a link to 4 online training modules. Each module consists of a 45–60-minute video presentation with interactive illustrative patient cases and integrated knowledge assessment with feedback. Each module contained 4 to 9 example patient cases that addressed particular key points. Questions about these cases are embedded in the flow of module information and participants must answer these questions to progress. At the end of each module, 5-6 questions to assess knowledge are presented. After each question, the correct answer is provided with explanation

Module #	Topic	Learning objectives
1	GDM Disease, Diagnosis and Complications	Define gestational diabetes (GDM) & how it is diagnosed in the United States. Compare changes in blood sugar control during normal pregnancy and GDM. Identify risk factors for GDM. Summarize the consequences for uncontrolled GDM for mom & baby.
2	Nutrition and Physical Activity Management	Define recommendations for weight gain during pregnancy. Describe types of nutrients and examples of each. Apply strategies for meal planning including cost concerns. Design alternative plans for different dietary preferences. Explain exercise recommendations during pregnancy. Create a patient-centered trimester-specific physical activity plan.
3	Monitoring, Medications, and Avoiding Hypoglycemia	Describe blood sugar monitoring recommendations and goals in women with GDM.

			
Identify the risks and common symptoms of hypoglycemia and determine appropriate treatment for these events.
 
Explain GDM treatment options including recommended medications.

4	Future Diabetes Risk and Prevention		
Assess patient's risk of future diabetes mellitus.
 
Describe current postpartum diabetes screening recommendations.
 
Construct a patient-centered plan to minimize risks of future diabetes mellitus.

### **6.1.2 Method of Assignment/Randomization**

Individuals were sequentially enrolled in a single study arm. There was no randomization.

### **6.1.3 Selection of Instruments/Outcome Measures**

See attached survey code book for reliability and validity statistics and references

## **6.2 Assessments**

### **6.2.1 Efficacy**

See attached surveys

### **6.2.2 Safety/Pregnancy-related policy**

There are no specific safety concerns in this study as this is an education intervention for healthcare staff, not patients.

#### **6.2.2.1 Adverse Events Definition and Reporting**

Individuals will be given contact information for study personnel to contact if there were concerns about training material or the study

## **6.3 Study Procedures**

### **6.3.1 Study Schedule**

Pre-test → Module 1 → Module 2 → Module 3 → Module 4 → Post-test

Individuals must complete pre and post tests and access all modules within 3 months to be eligible for Visa gift card drawing

### **6.3.2 Informed Consent**

A consent information sheet will be provided and individuals will be asked to confirm or decline participation in the research study. No written consent is required for this exempt study.

### **6.3.3 Screening**

Individuals will be allowed to participate if they self-identify as individuals involved in the care of women during gestational diabetes pregnancy.

### **6.3.4 Recruitment, Enrollment and Retention**

Modules are hosted online. Information about the availability of the modules will be distributed via email through multiple professional organizations to reach clinical staff providing care for women with GDM. Contacts at the following organizations will be emailed with a brief information form including a link to the modules: Nurse Family Partnership, MU Extension, St. Louis Regional Health Commission, St. Louis Integrated Health Network, Association of Women's Health, Obstetrics and Neonatal Nurses, National Association of Community Health Workers, National Association of Community Health Centers, Missouri Nurses Association, Generate Health, the Missouri Diabetes Shared Learning Network, Missouri Primary Care Association, American Public Health Association, and St. Louis community college community health worker and nurse training programs. Modules are eligible for nursing continuing education credits (1 credit per completed module) through Washington University. Information about the study with optional pre- and post-training assessments will be provided on the home page for the modules. Individuals will be asked if they agreed to participate in the study with a single question prior to completion of the

pre assessment. Individuals who complete the pre-assessment will receive a code to enter the first module and then a different code at the end of each module to enter the next module, and finally the post-assessment. The codes will be used to ensure individuals access all modules prior to completion of the post-assessment. Individuals completing modules within 3 months are eligible for drawing for a \$40 Visa gift card.

## **6.4 Statistical Method**

### **6.4.1 Statistical Design**

We plan a pre-post analysis of individual's scores on multiple continuous measures. For normally distributed data, a paired T test is planned. For non-normally distributed data, a Wilcoxon paired signed rank test is planned.

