### **6.4.2 Sample Size Considerations**

This was a pilot study and no a prior sample size calculation was completed.

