### **6.4.3 Planned Analyses**

#### **6.4.3.1 Primary Analyses**

For the primary outcome, we will compare scores on the self-efficacy for providing diabetes education before and after training among the individuals that complete the training.

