##### **6.4.4.2 Handling of Missing Data**

Individuals who do not complete the post assessment will not be included in the pre-post score comparison.

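### Does the primary analysis need a fixed test, a stated alpha and sidedness, and a confidence interval for the SEPDE change?

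*Combined protocol and SAP*

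**What the plan says.** All references are to the combined protocol and SAP.

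- **Outcome (5.2.1):** "The primary outcome is change in score on the self-efficacy to provide diabetes education questionnaire before and after completing the 4 module training". The Appendix entry for the SEPDE has 15 items and scores the scale as a mean over them.
- **Primary analysis (6.4.3.1):** "we will compare scores on the self-efficacy for providing diabetes education before and after training among the individuals that complete the training".
- **Method (6.4.1):** "For normally distributed data, a paired T test is planned. For non-normally distributed data, a Wilcoxon paired signed rank test is planned".
- **Analysed set (6.4.4.2):** "Individuals who do not complete the post assessment will not be included in the pre-post score comparison". Section 5.3.1 sets a recruitment target of 100, so the analysed number is 100 or fewer. No completion rate is projected.
- **Hypothesis (4.1):** "completing online interactive training modules on GDM will result in improved self-efficacy for providing diabetes education", which is worded as an improvement.
- **Sample size (6.4.2):** "This was a pilot study and no a prior sample size calculation was completed".
- **Reporting of numbers (6.4.3.2):** counts will be given for the pretest, each module and the post-test.

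The only alpha in the document is Cronbach's. No section states a significance level, the sidedness, a normality criterion, or an interval for the SEPDE change.

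**The concern.** Three things look open.

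1. **Size and precision.** This is a pilot with no sample size calculation and an unknown number of completers. Its main information is how large the change is and how well it is known, and a p value alone gives neither. A non-significant result could mean little change or too few completers.
2. **Alpha and sidedness.** The hypothesis predicts improvement, so someone could argue for a one-sided test after seeing the data. At a 5% level, a positive change with a two-sided p between 0.05 and 0.10 would then count as an improvement under one reading and not under the other.
3. **Choice of test.** Normality is to be judged, but the plan does not say how, or whether on the differences or the raw scores. The analyst could in principle choose between the two p values.

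If all three were exploited, the primary conclusion would depend on decisions made after the data were in.

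**Working it through.** The plan states no power, alpha or interval, so there is no figure to reproduce. The calculations below size each gap. They assume 30, 50 or 100 completers (only the target of 100 is in the document), roughly normal differences and a 5% level. Units are SDs of individual change, so no SEPDE response range is needed.

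**Step 1: precision.** The 95% half-width is t(0.975, n−1)/√n.

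| n | t(0.975, n−1) | Half-width | Interval when two-sided p = 0.05 |
|---|---|---|---|
| 30 | 2.045 | 2.045/√30 = 0.373 | 0 to 0.75 |
| 50 | 2.010 | 2.010/√50 = 0.284 | 0 to 0.57 |
| 100 | 1.984 | 1.984/√100 = 0.198 | 0 to 0.40 |

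The last column is 0 to twice the half-width. An interval is clearly worth reporting. Pre and post means and SDs alone would not supply it. The SD of change is the visit SD × √(2(1−r)), where r is the pre-post correlation (assumed). That is 1.183 at r = 0.3 and 0.632 at r = 0.8. At n = 50 the half-width is therefore 1.183 × 0.284 = 0.336 or 0.632 × 0.284 = 0.180 of the visit SD. However, a paired t test computes the mean difference and its standard error as part of the test. With the mean change, an exact p and n, the standard error is mean change/t(p), and the interval follows. Section 6.4.3.2 already plans to report how many complete the post-test.

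**Step 2: sidedness.** The chance of declaring improvement is the upper tail of the noncentral t with noncentrality d√n. The cut-off is t(0.975, n−1) for a two-sided test and t(0.95, n−1) for a one-sided test.

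| True change d | n | Two-sided 5% | One-sided 5% | Gap (points) |
|---|---|---|---|---|
| 0 | any | 2.5% | 5.0% | 2.5 |
| 0.3 | 30 | 35.5% | 48.4% | 12.9 |
| 0.3 | 50 | 54.8% | 67.3% | 12.5 |
| 0.3 | 100 | 84.4% | 90.9% | 6.5 |
| 0.5 | 50 | 93.4% | 96.7% | 3.3 |
| 0.5 | 100 | 99.9% | 100.0% | 0.1 |

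The largest gap found for d from 0 to 0.5 is 13.2 points (n = 30, d = 0.35). It arises only if someone adopts a one-sided test, which no section of the plan mentions. A directional hypothesis does not imply one.

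**Step 3: choice of test.** One simulation assumed 15 items rounded and clipped to a 1-5 scale, baseline means of 3.5 or 4.2, gains of 0, 10% or 20% of the remaining room, and 2,000 to 3,000 runs per setting.

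- With no change, the t test and signed-rank test rejected in 4.3% to 5.3% of runs.
- The largest power difference was 79.8% against 73.8%, or 6 points.
- Checking normality on raw scores instead of differences altered significance in at most 5.6% of runs.

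A second simulation used normal differences with no change (10,000 runs) and deliberately took whichever test was significant. It gave 6.2% at n = 50 and 5.6% at n = 100.

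**Step 4: which data are checked for normality.** Both tests are paired, and the outcome is a change. The natural reading is that normality is judged on the within-person differences.

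**The case for a change.** The strongest case for a change is that the fix is one sentence, needs no new data, and removes any doubt. If two-sided 5% is the convention, writing it down costs nothing. The plan does list summary statistics for subject characteristics in 6.4.3.3, yet none for the primary change. Test choice is also not always harmless. With skewed differences whose true mean is zero (shifted gamma, shape 4; Shapiro-Wilk at 5%), choosing the test by a normality check rejected 9.7% of the time at n = 50 and 13.0% at n = 100, against about 5.7% for the t test alone.

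Part of this stands. The details are absent, and stating them would be good practice. The rest is weaker.

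- Section 6.4.3.3 covers subject characteristics, so its list says nothing about how outcomes will be reported. A mean change is implied by the named outcome and the scoring rule.
- The 9.7% and 13.0% are not false-positive rates for training that has no effect. In that case pre and post scores are exchangeable, so the differences are symmetric and the signed-rank test is valid. Skewed differences with mean zero mean that some people change and others change in the opposite direction. Signed-rank does not test the mean there, and detecting such a pattern is not the same as finding an effect where there is none.
- Naming signed-rank in advance, with a matching estimate and interval, would close the gap equally well. The argument for the t test is therefore a preference and not a correction.

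**Conclusion.** No change is needed. The plan omits alpha, sidedness, a normality criterion and a planned interval, but it names the outcome, the analysed set, two suitable paired tests and a rule for choosing between them. Followed as written, it gives a sound paired comparison, and analysts would be expected to fill the gaps with a two-sided 5% level, normality judged on the differences, and the SEPDE change reported with a 95% interval. No stated figure is wrong.

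The largest effect of a different reading is about 13 points in the chance of declaring improvement, and it requires a one-sided test that nothing in the plan supports. The choice between the two tests moves power by at most 6 points in the settings run. These sizes rest on assumed completer numbers, effect sizes and a 1-5 scale model. They are results for those settings and not bounds. A sentence in 6.4.3.1 stating the level, the sidedness and the interval would be a harmless clarification, but the analysis does not depend on it.
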